5. STUDY INTERVENTIONS

In-Person Treatment for all participants will follow the Mindfulness-Based Addiction Treatment (MBAT) group protocol (Wetter et al., 2009). MBAT groups will only contain study participants (i.e., MBAT groups will not involve existing classes apart from the study). Studies of mindfulness treatments have typically utilized a group format (Keng, Smoski, & Robins, 2011; Roemer & Orsillo, 2003), and the approaches in this study are particularly well suited to a group format. Not only may the group format facilitate the acquisition of skills through observational learning and practice, but it may also increase participants' willingness to explore different practices more than they would have on their own. Thus, we chose to include group treatment (rather than delivering the entire treatment via text-messaging, which would lack important aspects of group treatment). All participants receive nicotine replacement therapy (NRT) and self-help materials in addition to MBAT. Participants receive nicotine patch therapy because the patch is the most widely used pharmacotherapy for smoking cessation and the *Treating Tobacco Use and Dependence Clinical Practice Guideline* identified the patch as a frontline therapy.(Fiore et al., 2000; Fiore et al., 2008) Compared to bupropion and varenicline, the patch is safer, better tolerated, and available over-the-counter.

Therapists. There will be between 1 and 3 therapists (depending on therapist schedules). Minimum therapist qualifications are: 1) completion of master's degree or equivalent in counseling, psychology, social work, or related field; 2) daily mindfulness practice; 3) experience teaching stress reduction or body-centered awareness disciplines in a group setting; and 4) completion of formal training in mindfulness (e.g., the 7-day residential Professional Training Program in Mindfulness-Based Stress Reduction or the 5-day Mindfulness-Based Cognitive Therapy professional training). Sessions will be audio-recorded in order to allow for assessment of treatment fidelity. After each session, audio recordings will be uploaded onto a secure server and deleted from the recorder. The server is managed by Georgia State University, password-protected, and available only to research personnel who have completed training in research with human subjects. [name] will randomly select two sessions from each group and rate adherence to the protocol using a modified version of the MBCT Adherence Scale (Segal, Teasdale, Williams, & Gemar, 2002; reference to depression will be replaced with reference to smoking). Each item is rated on a 0 to 2 point scale (0 = no evidence for item, 1 = slight evidence, 2 = definite evidence). For any items rated as 0 or 1, [name] will conduct further training with the study therapist.

Nicotine Patch Therapy. Patch therapy (beginning the week before quit day) for participants who smoke >10 cigarettes/day will consist of 4 weeks of 21 mg patches, 1 week of 14 mg patches, and 1 week of 7 mg patches. Patch therapy for participants who smoke 5-10 cigarettes/day will consist of 4 weeks of 14 mg patches and 2 weeks of 7 mg patches. Patch dispensation will occur at weekly visits. Participants receive only the number of patches necessary to last until the next study visit plus several extra patches should a patch fall off, become torn, or should the visit be delayed. Based on our previous research, providing participants with only enough patches to last until the subsequent visit improves compliance.

Self-Help Materials. All participants will also be given evidence-based self-help materials for smoking cessation (based on the *Treating Tobacco Use and Dependence Clinical Practice Guideline* (Fiore et al., 2008).

MBAT Overview. Group treatment will strictly follow the MBAT protocol developed and used by [name]. MBAT closely follows Mindfulness-based Cognitive Therapy (MBCT) procedures, but

replaces the depression-related material with nicotine dependence-related material. MBAT consists of 8 weekly 2-hour sessions (Wetter et al., 2009). The core aims are to help participants: 1) become more aware of thoughts, feelings, and sensations from moment to moment, 2) develop a different way of relating to thoughts, feelings, and sensations, and 3) obtain the ability to disengage attention and choose skillful responses to thoughts, feelings, and situations. In order to provide additional support on the quit date and encourage further mindfulness practice, session 5 (quit date) will be an extended 4-hour session.

MBAT emphasizes daily practice in several forms: formal sitting meditation, body scan meditation, walking meditation, eating meditation, and gentle yoga. Each of these practices shares a focus on awareness of the breath. By offering a menu of practices, differing preferences and learning styles can be accommodated. The quit day is scheduled for Session 5. Sessions 5-8 focus on continued development of awareness of the present, along with expansion of techniques for dealing with problematic thoughts, feelings, and situations. The group leader will have: 1) at least a master's degree or equivalent in counseling, psychology, social work, or a related field; 2) a regular personal mindfulness practice; 3) experience teaching mindfulness in a group setting; and 4) completion of training in teaching mindfulness.

Text Messages. Participants in the iQuit Mindfully condition will receive text messages on each day between treatment sessions. These messages are based on the MBAT protocol, the Text2Quit program led by [name] (Abroms et al., 2012), and the SmokefreeTXT program developed by the National Cancer Institute (some of the messages are directly from the SmokeFreeTXT library). The content and frequency of messages were revised based on focus groups in low-income, racially diverse smokers. Text messages will remind participants to practice mindfulness (e.g., reminders for informal practice, such as awareness of the breath throughout the day, and reminders for formal practice such as the body scan and sitting meditation). Text messages will also remind participants of their personal reasons to quit as well as specific strategies to aid in cessation (e.g., reminders to get rid of cues to smoke, reach out for social support, and use cognitive-behavioral strategies taught in MBAT).

Participants will receive approximately 2 messages per day during Week 1, 3/day during Week 2, 4/day during Week 3, 5/day during Week 4, 6/day during Week 5, 4/day during Week 6, and 3/day during Week 7 (these numbers could be revised based on participant feedback). In addition, as in Text2Quit and SmokefreeTXT, participants will be able to text specified words to request help. Specifically, they may text CRAVE, STRESS, or SLIP at any point to receive additional text message support for coping with cravings, stress, or smoking lapses, respectively. Participants will also receive a relatively small number of texts (1-3 per week; exact number to be determined based on pilot project) during the 1-month follow-up period, and they will also have the opportunity to text keywords (CRAVE, STRESS, SLIP) during this time.

Mobile Commons, a service that supports the development and implementation of automated SMS applications, will be used to build the automated text message system and send and receive the text messages. Participants will receive text messages and will also have the option of texting CRAVE, STRESS, or SLIP.

Adherence. Adherence is defined as the number of intervention sessions attended and amount of mindfulness practice between sessions. Secondary analyses will examine associations between these adherence variables and abstinence outcomes.

Financial Compensation and Retention Procedures. Participants will be compensated for each of the 9 in-person visits in which they complete assessments after baseline (8 treatment sessions and 1 follow-up; \$25 for assessments at session 1-4 and 6-7 visits; \$40 for session 5 assessment; \$50 for post-treatment assessment; and \$50 for follow-up assessment (assessments on session 5, post-

treatment, and follow-up are longer than other sessions and thus associated with higher compensation). Participants will be compensated with \$10 for completing at least 7 of the 10 daily assessments around the quit date (to be paid at session 6 visit). The maximum compensation per participant will be \$300. Other procedures to increase adherence include: 1) reminder phone calls and letters, 2) requiring a phone number and valid home address so that participants can be contacted, and 3) obtaining names, addresses, and phone numbers of up to three collaterals who can provide information on participants' whereabouts if necessary. Written permission to contact the collaterals will be obtained from participants. Participants who do not attend in-person assessment visits will be contacted via phone, email, text message, and/or mail to reschedule or (if not able to reschedule) provide self-reported smoking status and feedback about the program/reasons for discontinuation.

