1. STUDY OBJECTIVES

Primary outcomes for this development and feasibility study are: 1) feasibility (e.g., attrition, engagement, participant ratings; specific definitions of these outcomes are described in section 9), 2) determining best practice for implementing and refining the text-messaging intervention (e.g., how many texts per day and at what times of day; which types of messages are most helpful; ways of increasing adherence), and 3) an estimate of effect size (based on smoking cessation in iQuit Mindfully vs. MBAT). Effect sizes will be of greater importance than statistical significance, given that this is a feasibility study. Secondary analyses will include: 1) effects of treatment conditions on average number of cigarettes smoked per day; 2) effects of treatment on weekly mindfulness practice; 3) effects of treatment on self-reported levels of mindfulness, affect, self-efficacy, coping, dependence, and withdrawal symptoms; and 4) associations between number of sessions attended, weekly mindfulness practice, and abstinence.

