Daily Surveys around Quit Date. In order to gather more daily data about emotions, smoking, and mindfulness surrounding the quit date, all participants will be asked to complete a daily online survey for 10 days surrounding the quit date (Days 3, 2, 1 pre-quit, Quit Date, and Days 1-6 post-quit). Each morning, participants will be sent a link (via text, and also via email for participants who supply an email address) to an online survey including 8 questions about emotions, smoking, and mindfulness on the previous day.

Follow-Up Visit and Individual Interview. One month following the last treatment session, participants will attend an in-person follow-up visit in which they will complete questionnaires, provide expired CO samples, and complete an individual interview. Individual interviews will be conducted by trained research staff. All participants will be asked for their feedback about and suggestions for improving the intervention. In addition, interviews with iQuit Mindfully participants will involve more in-depth discussion of what participants liked/did not like about the texts, how they perceived the messages to be helpful/unhelpful, and their suggestions for improving the text-based program. Interviews will be audio-recorded with a digital voice recorder and transcribed verbatim.

Blinding

The majority of study personnel, including the PI, will be blinded to treatment condition until the database is locked. Limited staff will be unblinded to handle randomization codes, administer individual interviews (i.e., the graduate research assistant) and delivery of interventions (i.e., the study therapist). Once the algorithm for randomization has been prepared, the graduate research assistant will execute the randomization scheme. The graduate research assistant (unblinded) will also be responsible for preparing reports for data and safety monitoring, as well as conducting individual interviews (which requires knowledge of the participants' treatment conditions). Research personnel who are blinded to treatment condition will administer all assessments. For example, in order for participants to complete the post-treatment assessment, separate research personnel (who do not know the treatment condition) will arrive after the treatment ends and administer the assessments.

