9. STATISTICAL CONSIDERATIONS AND DATA ANALYSES

Primary outcomes for this development and feasibility study are: 1) feasibility (e.g., attrition, engagement, participant ratings), 2) determining best practice for implementing and refining the text-messaging intervention (e.g., how many texts per day and at what times of day; which types of messages are most helpful; ways of increasing adherence; these variables will be assessed through participant feedback in the individual interview and final program evaluation questionnaire), and 3) an estimate of effect size (based on smoking cessation in iQuit Mindfully vs. MBAT).

Approximately 35% attrition will be deemed acceptable (based on 34% attrition in Vidrine et al.'s (2016) trial of mindfulness-based smoking cessation treatment). Level of engagement will be determined based on: 1) the proportion of texts that participants indicate reading (we expect that at least 75% will read most or all texts, based on Abroms et al.'s (2012) findings); and 2) responses to interactive text messages (we expect that at least 85% of participants will respond to at least one of the interactive text messages or use the CRAVE, STRESS, or SLIP keywords at least once, based on Heminger et al.'s (2016) findings). In terms of participant ratings, we will focus on ratings of helpfulness of the text messages and the extent to which participants would recommend the text messaging program to others (rated on 1-10 scales; the minimum acceptable rating is 6).

Effect sizes will be of greater importance than statistical significance, given that this is a feasibility study. Smoking abstinence will be defined as self-reported complete abstinence for 7 days that is biochemically confirmed with expired carbon monoxide <6ppm. Chi-square tests and t-tests will be used to evaluate group differences.

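### End-of-treatment abstinence is routinely CO-confirmed at Session 8, which also counts as a session attended, so scoring missing CO as smoking creates a positive attendance–abstinence association even if none exists

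*Combined protocol and SAP*

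**What the plan says.** Section 5 (Adherence): "Adherence is defined as the number of intervention sessions attended and amount of mindfulness practice between sessions". It continues: "Secondary analyses will examine associations between these adherence variables and abstinence outcomes". Section 1 lists the same analysis as the fourth secondary one: "associations between number of sessions attended, weekly mindfulness practice, and abstinence". Section 5 (MBAT Overview) fixes the number of sessions: "MBAT consists of 8 weekly 2-hour sessions". Session 8 is not excluded from the count.

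Section 9 defines abstinence as "self-reported complete abstinence for 7 days that is biochemically confirmed with expired carbon monoxide <6ppm".

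Section 5 (Financial Compensation and Retention Procedures) pays participants for "each of the 9 in-person visits in which they complete assessments after baseline (8 treatment sessions and 1 follow-up"). The same paragraph says that people who miss an in-person assessment are contacted to reschedule and, failing that, to report their smoking status themselves.

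Section 6 (Blinding) has separate, blinded staff do the post-treatment assessment; they "will arrive after the treatment ends and administer the assessments". Section 6 also provides a CO sample at a follow-up visit one month after the last session.

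For secondary analysis 4 the plan gives no time point, no model, no rule for scoring abstinence when CO is missing, and no statement on whether Session 8 counts as exposure for the end-of-treatment outcome.

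**The concern.** At end of treatment, exposure and outcome share a visit. Attending Session 8 adds one to the session count and is also the routine way to be recorded as abstinent. People who drop out earlier have low counts and, unless they reschedule, no CO reading. If no reading means not abstinent, attendance helps decide whether abstinence can be recorded at all. This is a different problem from relapse leading people to stop attending: it arises even when smoking and attendance are unrelated.

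The trial's rationale in section 2 is that engagement and practice between sessions help people quit. A positive attendance–abstinence correlation would naturally be read as support for that, when some or all of it could come from how the outcome is ascertained.

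**Working it through.** **1. Where the end-of-treatment sample is taken.** The payment list gives six visits for Sessions 1–4 and 6–7, one for Session 5, one post-treatment and one follow-up: 6 + 1 + 1 + 1 = 9, the stated number. The amounts are 6 × 25 + 40 + 50 + 50 + 10 = 300 dollars, the stated maximum. With "8 treatment sessions and 1 follow-up" as the only post-baseline visits, both totals close only if the post-treatment assessment is the Session 8 visit.

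**2. The mechanism.** Let S be sessions attended, A8 attendance at Session 8 (0/1), p the true abstinence rate, unrelated to attendance, and f the share of Session 8 absentees who give CO at a rescheduled visit. Let R be recorded abstinence, with missing CO scored as smoking.

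- P(R = 1 | present) = p and P(R = 1 | absent) = p·f.
- Hence Cov(S, R) = p(1 − f)·Cov(S, A8). This is positive whenever f < 1, because S includes A8.
- With p = 0.30, recorded abstinence is 30% in attenders of Session 8. In absentees it is 0% if f = 0, and 0.30 × 0.5 = 15% if f = 0.5.

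**3. Size by simulation.** From the documents: N = 70 (section 3) and 35% attrition. Section 9 gives the latter only as an acceptable level and does not tie it to Session 8. Assumed: constant dropout to 35% by Session 8; 95% attendance while enrolled (so 0.65 × 0.95 = 62% present at Session 8); p = 20/30/40%; a two-sided 5% test of S against R.

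| Absentees giving rescheduled CO | Mean r | False positives at p = 20/30/40% |
|---|---|---|
| 0% | about 0.24–0.36 | about 50/90/99% |
| 25% | not tabulated | about 22/45/62% |
| 50% | about 0.10–0.16 | about 11/18/26% |
| 75% | not tabulated | about 6/7/9% |

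With 20% dropout, false positives are about 15–17/51–54/82–84% with no rescheduling and about 6/11/19% with half rescheduled.

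**4. Sensitivity to the attendance pattern.** Now take 65% attendance at each session, no rescheduling, and p = 15/25/40%. If sessions are missed independently of one another, r = 0.09, 0.12 and 0.16. If attendance is clustered within person, r = 0.16, 0.22 and 0.30.

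**5. Alternatives under the same null.**

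- *Count Sessions 1–7 only, missing CO = smoking, no rescheduling.* With constant dropout, false positives are still about 35/72/94%. The step is sufficient only if sessions are missed independently (r about 0); with clustered attendance r is 0.14–0.25.
- *CO-available participants only.* r is about 0 and false positives about 4–6%. With constant dropout and no rescheduling, however, none of the people analysed had attended four or fewer sessions.
- *Self-report including missed-visit contacts, unknown status left out.* False positives are about 4–5% if half of absentees are reached regardless of smoking. If 70% of absent abstainers but 40% of absent smokers are reached, mean r is about −0.07 to −0.10 and false positives roughly 9–13%.
- *1-month outcome, missing = smoking.* r is about 0 with independent attendance and 0.14–0.25 with clustered attendance.

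**The case against.** The strongest reply is that the association is conditional, and that stands. A reader might infer that end-of-treatment abstinence can be confirmed only at Session 8; the rescheduling provision in section 5 contradicts this. A reader might also infer that the bias is inevitable. It needs missing CO to be scored as not abstinent, and no section states that rule. The literal definition in section 9 leads there, and the plan offers no other rule, but an analysis of people with a CO result avoids the artefact.

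It is equally tempting to quote the 50–99% false-positive figures as the expected result. They assume that rescheduling never succeeds, and the documents give no rate for it. Rescheduling shrinks the artefact but does not remove it unless every absentee gives a sample. Section 5 itself foresees people who cannot reschedule and give self-report only.

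Secondary analysis 4 is also not tied to end of treatment. The 1-month visit is not an intervention session, so that outcome shares no visit with the exposure; it is affected only if dropout persists and missing is scored as smoking.

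Finally, this is one secondary association in a feasibility pilot that ranks effect sizes above significance. That limits the consequences, but r itself is an effect size and is what is distorted. Nothing here bears on the randomised comparison of arms.

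**Conclusion.** The point holds in conditional form. If secondary analysis 4 is done at end of treatment, with all eight sessions counted and the abstinence definition applied literally, it has a partly built-in positive association between attendance and abstinence. With N = 70 and 35% dropout by Session 8, the artefact is a mean r of about 0.24–0.36 with no rescheduling and about 0.10–0.16 with half of absentees rescheduled. It is about zero among people with a CO result, but few or no low attenders then remain unless absentees are rescheduled.

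The sizes rest on assumed true abstinence, dropout pattern, rescheduling rate and test level, and on applying the 35% to Session 8. The effect on the mindfulness-practice measure was not computed, so no size is claimed for it. The plan should be changed because the remedy is cheap and the biased result would agree with the trial's own hypothesis.

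**What to change.** In section 9, for secondary analysis 4, state the time point. For the end-of-treatment outcome, count Sessions 1–7 as the exposure and include arm as a term. Keep CO-confirmed abstinence, but report three versions side by side:

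1. missing CO scored as smoking;
2. participants with a CO result only, including rescheduled visits;
3. self-reported 7-day abstinence, including the missed-visit contacts already planned in section 5, with unknown status left out.

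Say that the first version has a partly built-in positive association, and interpret an association only if it holds across all three. Dropping Session 8 from the count is not enough by itself.

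The cost is a few sentences and a little more analysis, with no new data. Version 2 says little about low attenders. Version 3 is unconfirmed, and is biased if response among absentees depends on whether they smoke. That is why it should stand beside the CO-confirmed versions and not replace them.

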6. STUDY PROCEDURES

Screening Evaluation and Consenting Procedure

Telephone Screening. Interested individuals will be given a detailed description of the study over the phone. The voluntary nature of the study will be emphasized, and it will be made clear that if they decide not to participate, there will be no repercussions. Research staff will read the telephone consent form to potential participants and answer any questions. After provision of verbal informed consent (a Waiver of Documentation of Consent has been included in the GSU IRB protocol), the research staff member will document verbal consent and sign and date the consent form. Potential participants will then be screened for inclusion/exclusion and answer questions about demographic information. Eligible individuals who are interested in participating will be scheduled for an initial in-person session. Participants will receive a reminder telephone call, text, and/or email on the day before their scheduled session.

In-Person Baseline Visit and Consent Procedure. Following the phone screen, interested individuals will attend an in-person session to finalize eligibility, engage in further discussion about the study, and provide written informed consent.

Before in-person assessment of eligibility criteria, participants will review the consent form for in-person screening. Study personnel will offer an opportunity for participants to ask questions and have them answered, the consent form for in-person screening will be signed and dated by the participant and staff member, and a copy of this form will be given to the participants. Then, in order to confirm eligibility, participants will provide a breath sample for assessment of expired carbon monoxide. Health literacy will be assessed with the Rapid Estimate of Adult Literacy in Medicine (REALM; Davis et al., 1991), and for the proposed study participants who have at least a sixth-grade level will be eligible. Individuals who decline or are ineligible will be given self-help materials and referral to other cessation programs. In addition, potential participants will complete the Patient Health Questionnaire-2 (PHQ-2; Kroenke, Spitzer, & Williams, 2003; Lowe, Kroenke, & Grawe, 2005) and answer a question regarding psychotic disorders in order to screen for clinically significant depressive symptoms and psychotic disorders, respectively. Individuals who are not eligible for these reasons will be provided with appropriate mental health referrals in addition to smoking cessation referrals.

Next, the research staff will engage eligible individuals in a discussion of pros and cons of participating, as well as participants' ambivalence about behavior change and research participation (these methods have been suggested to improve retention; Goldberg & Kiernan, 2005).

For eligible individuals who are interested in participating, study personnel will initiate the informed consent process which will include: 1) A thorough review of the Informed Consent Form (ICF), particularly study procedures; 2) Study personnel will offer an opportunity for participants to ask

questions and have them answered; 3) The ICF will be signed and dated by the participant and staff member; and 4) A copy of the ICF will be given to the participants.

Study personnel will explain the text messaging procedures in detail and send a test message to the participant, who will respond and ask any questions. Participants will indicate when they typically wake up and when they typically go to bed. This information will be used so that text messages will only be sent during the hours specified by each individual participant.

Individuals who would like to participate and express informed consent will then be asked to complete questionnaires. Descriptions of the assessments are provided below:

- The *Telephone Screening* assesses eligibility criteria and demographic characteristics, including age, race, ethnicity, education, employment, and income.
- *Tobacco History* assesses onset of regular smoking, previous quit attempts, abstinence history, smoking rate, and partner smoking status. This includes the *Heaviness of Smoking Index* comprises two items from the *Fagerström Test for Nicotine Dependence* (FTND) (Heatherton, Kozlowski, Frecker, & Fagerstrom, 1991): self-reported average number of cigarettes smoked per day and time to first cigarette upon waking (“time to first cigarette”). The HSI is a strong indicator of nicotine dependence (Kozlowski, Porter, Orleans, Pope, & Heatherton, 1994).
- The *Rapid Estimate of Adult Literacy in Medicine* (REALM)(Davis et al., 1991) is a rapid screening instrument that is used to assess health literacy. It takes 2-3 minutes to administer and score and is highly correlated with comprehensive literacy diagnostic instruments. Individuals are classified as having limited (\leq 6th grade reading level; REALM=0 to 44), marginal (7th- to 8th-grade reading level; REALM=45 to 60), or adequate (\geq 9th grade reading level; REALM=61 to 66) health literacy skills. Participants with scores \leq 44 will be excluded from the proposed study.
- In order to assess for *current psychotic disorders*, participants will be asked, “Do you have a current diagnosis of Schizophrenia or Bipolar Disorder or take anti-psychotic medications such as Haldol or Thorazine?”. Individuals who answer affirmatively will not be eligible but will be provided with appropriate mental health referrals.
- The *Patient Health Questionnaire-2* (PHQ-2; Kroenke et al., 2003; Lowe et al., 2005) is a 2-item questionnaire designed to screen for symptoms of depression. Participants are asked, “Over the last 2 weeks, how often have you been bothered by the following problems?”: “feeling down, depressed or hopeless” and “little interest or pleasure in doing things.” These items (which correspond to the two core diagnostic criteria for Major Depressive Disorder; APA, 2013) are rated on a 0-3 scale (0 = not at all, 3 = nearly every day). Individuals with scores of 3 or above (which has been identified as the cut-off for obtaining optimal sensitivity and specificity for identifying depressive disorders; Kroenke et al., 2003; Lowe et al., 2005) will not be eligible but will be provided with appropriate mental health referrals.
- *Smoking Status (SRNT)* surveys tobacco use, use of other tobacco products, and nicotine replacement medications. The questionnaire also collects data on the use of other tobacco products and nicotine replacement medications as determined by the participant's time point in the protocol (e.g., based upon the date the participant quits smoking) (Hughes et al., 2003). Point prevalence abstinence (i.e., no smoking during past week) will be self-reported and biochemically confirmed by CO<6ppm.
- The *Brief Wisconsin Dependence Motives Questionnaire* (Smith, Piper et al., 2011) is a 37-item measures that yields an overall dependence score and subscale scores for other dimensions (i.e., cognitive enhancement, affective enhancement, automaticity, affiliative

attachment, loss of control, craving, cue exposure/associative processes, social/environmental goals, taste/sensory processes, weight control, tolerance).

- The *Wisconsin Smoking Withdrawal Scale* (Welsch et al., 1999) includes subscales for anger, anxiety, sadness, concentration difficulty, craving, hunger, and sleep. All subscales have excellent internal consistency and validity (Wetter et al., 2000).
- The *Self-Efficacy Scale* assesses confidence for resisting smoking urges in specific types of situations (e.g., when feeling stressed, when with friends) (Condiotte & Lichtenstein, 1981) Subscales include negative affect, pleasure, social image, social influence, and diet. Scores are predictive of relapse (Cinciripini, Cinciripini, Wallfisch, Haque, & Van Vunakis, 1996).
- The *Mindful Attention Awareness Scale* (MAAS; Brown & Ryan, 2003) is a 15-item self-report measure of dispositional mindfulness that has shown good reliability and validity.(Brown & Ryan, 2003)
- The *Five-Factor Mindfulness Questionnaire- Short Form* (FFMQ-SF; Bohlmeijer, ten Klooster, Fledderus, Veenhof, & Baer, 2011) is a 24-item self-report questionnaire of facets of dispositional mindfulness. The scale yields five factors: 1) Nonreactivity, 2) Observing, 3) Acting with Awareness, 4) Describing/Labeling with Words, and 5) Nonjudging of Experience. The FFMQ-SF correlates highly with the 39-item FFMQ and has comparable internal consistency and factor structure.
- Participants will fill out a *Weekly Mindfulness Practice Log* (Vidrine et al., 2016) to indicate how frequently they practice each of the mindfulness techniques taught in treatment.
- The *Perceived Stress Scale – Short Form* (Wartig, Forshaw, South, & White, 2013) is a 4-item self-report measure of the extent to which individuals view their lives as stressful. The scale shows good psychometric properties.
- The *Positive and Negative Affect Schedule* (PANAS (Watson, Clark, & Tellegen, 1988)) is a 20-item self-report measure of affective experience yielding two factors (Positive and Negative Affect) with strong psychometric properties (Watson et al., 1988).
- Participants in the iQuit Mindfully group will be asked to provide weekly feedback about their experiences receiving the text messages (*Weekly Text Message Feedback*), and both groups will complete *Final Program Evaluation*. Items will assess perceived helpfulness and acceptability of the in-person and text messaging portions of treatment and also solicit suggestions for improving future programs.

The maximum time between telephone screening and enrollment will be 1 month. The maximum time between baseline assessment (as well as randomization, which will occur right after baseline assessment) and start of treatment will be 1 month. However, we will employ a variety of strategies to ensure that these timeframes are as short as possible. For example, in order to reduce the time between telephone screening and baseline we will offer a variety of days and times for baseline assessment. We will also time our recruitment efforts around planned baseline assessments to maximize potential participants' interest (in order to prevent longer wait time to accrue a sufficient number of participants to start a group).

Daily Surveys around Quit Date. In order to gather more daily data about emotions, smoking, and mindfulness surrounding the quit date, all participants will be asked to complete a daily online survey for 10 days surrounding the quit date (Days 3, 2, 1 pre-quit, Quit Date, and Days 1-6 post-quit). Each morning, participants will be sent a link (via text, and also via email for participants who supply an email address) to an online survey including 8 questions about emotions, smoking, and mindfulness on the previous day.

Follow-Up Visit and Individual Interview. One month following the last treatment session, participants will attend an in-person follow-up visit in which they will complete questionnaires, provide expired CO samples, and complete an individual interview. Individual interviews will be conducted by trained research staff. All participants will be asked for their feedback about and suggestions for improving the intervention. In addition, interviews with iQuit Mindfully participants will involve more in-depth discussion of what participants liked/did not like about the texts, how they perceived the messages to be helpful/unhelpful, and their suggestions for improving the text-based program. Interviews will be audio-recorded with a digital voice recorder and transcribed verbatim.

Blinding

The majority of study personnel, including the PI, will be blinded to treatment condition until the database is locked. Limited staff will be unblinded to handle randomization codes, administer individual interviews (i.e., the graduate research assistant) and delivery of interventions (i.e., the study therapist). Once the algorithm for randomization has been prepared, the graduate research assistant will execute the randomization scheme. The graduate research assistant (unblinded) will also be responsible for preparing reports for data and safety monitoring, as well as conducting individual interviews (which requires knowledge of the participants' treatment conditions). Research personnel who are blinded to treatment condition will administer all assessments. For example, in order for participants to complete the post-treatment assessment, separate research personnel (who do not know the treatment condition) will arrive after the treatment ends and administer the assessments.

